4.2.2 Definition of concomitant medication in case of missing dates

The following rules for classifying medication as prior or concomitant will be applied in the case of completely missing stop and/or start date information:

Table 4-1: Rules for assignment of medication in case of missing start and/or stop dates			
Start date	Stop date	Prior medication	Concomitant medication
Missing	Missing	Yes	Yes
Missing	Before start date of LCM	Yes	No
Missing	After start date of LCM	Yes	Yes

Table 4-1: Rules for assignment of medication in case of missing start and/or stop dates

Start date	Stop date	Prior medication	Concomitant medication
Before or on start date of LCM	Missing	Yes	Yes
After start date of LCM	Missing	No	Yes

In patient data listings, dates will be displayed as reported.

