4.2.1 Incomplete dates for medication and ADRs

In order to classify medication as prior or concomitant or to classify an ADR as treatment emergent, a complete date must be established. For the purposes of imputing missing components of partially-reported start and stop dates for medication use or ADRs, the algorithms listed below will be followed. Start and stop dates will be displayed as reported in the patient data listings (ie, no imputed values will be displayed in data listings).

- Missing start day but month and year present:

If the start of LCM occurred in the same month and year as the start of the medication or ADR, the start day of the medication or ADR will be assigned to the day of first administration of LCM.

Otherwise the start day will be set to the 1st day of the month.

- Missing start day and month but year present:

If the start of LCM occurred in the same year as the start of the medication or ADR, the start day and month will be assigned to the date of first administration of medication.

Otherwise the start day and month will be set to January 1st.

- Missing end day but month and year present:

The end day will be set to the last day of the month.

- Missing end day and month but year present:

The end day and month will be set to the date of study termination. However, if the study termination year is greater than the medication or ADR end year, the day and month are to be set to December 31st.

- Missing year but month or day and month present:

The rules as described in Section 4.2.2 will be followed.

If the end date is completely missing, then the medication or ADR are assumed to be ongoing.

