4.2.3 General imputation rule for incomplete dates

Where necessary for the calculation of derived variables, partial dates will be completed using the earliest calendar date based on the partial date provided. This rule is valid for all partial dates with the exception of the following:

- Year is missing
- Start and stop dates of ADRs
- Start and stop dates of medications (see Sections 4.2.1 and 4.2.2)
- Start and stop dates of LCM
- Date of final contact
- Date of premature discontinuation

Incomplete dates for final contact and premature discontinuation, respectively, will be completed using the latest calendar date based on the partial date provided.

Start and stop dates of ADRs and LCM will not be imputed.

Completely missing dates or dates with a missing year will not be replaced, and the corresponding derived variables will be set to missing.

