4.8 Examination of subgroups

The primary endpoints will be summarized by the following subgroups, if at least 25 patients fall into that subgroup:

- Starting dose of LCM (high starting dose - first dose ≥ 200 mg/day; titration – first dose < 200 mg/day)
- Prior tumor treatment (radiotherapy; chemotherapy; surgery; radiotherapy and chemotherapy; radiotherapy and surgery; chemotherapy and surgery; radiotherapy, chemotherapy and surgery)
- Concomitant tumor treatment (radiotherapy; chemotherapy; surgery; radiotherapy and chemotherapy; radiotherapy and surgery; chemotherapy and surgery; radiotherapy, chemotherapy and surgery)
- Number of different types of lifetime AEDs (1; 2; 3; 4)
- Core AED therapy (including but not limited to levitiracetam, valproate sodium, lamotrigine, oxcarbazepine, zonisamide, topiramate, pregabalin, gabapentin, phenytoin, carbamazepine, clonazepam, clobazepam, phenobarbital, valproic acid, ergenyl chrono; combinations of these therapies)

Note: Each subject can be only in 1 category for "Core AED therapy"

- Age (≥ 16 - ≤ 18 ; > 18 - < 65 ; ≥ 65)
- Sex (male; female)
- Historical seizure frequency (1; 2-5; 6+)
- Historical seizure type (Partial-onset seizures with secondary generalization; Partial-onset seizures without secondary generalization; Both)
- Time since tumor diagnosis (≤ 1 month; > 1 - ≤ 3 months; > 3 - ≤ 6 months; > 6 months - ≤ 12 months; > 12 - ≤ 24 months; > 24 months)
- Type of brain tumor (astrocytoma; oligodendrolioma; mixed [oligo-astro]; ependymoma; other)
- WHO grade (1; 2; 3; 4)
- Karnofsky performance status (<60%; 60%; 70%; 80%; 90%; 100%)

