6.4 Prior and concomitant medications

The number and percentage of patients who used prior and concomitant medications (including chemotherapy and AEDs) will be summarized according to the anatomical therapeutic class main group, the therapeutic subgroup, and the generic drug name.

Prior medications are those medications started before the first dose of study drug. Medication taken after the first dose of study medication will be regarded as concomitant medication whether the start date is before, after or on the date of the first dose of study medication. Lifetime AEDs are AEDs with an end date before the first dose of study drug.

The core AED will be summarized separately using the “Core AED?” question on the CRF to select the relevant medications. The core AEDs are the AEDs that the patient is receiving at Baseline.

The number and percentage of patients according to Core AED therapies will be summarized according to preferred term combination.

The number and percentage of patients who had prior or concomitant radiotherapy will be summarized. The total dose in gray (Gy) and number of fractions will be summarized as continuous variables.

Rules for defining concomitant medications with missing dates are provided in [4.2.2](#).

All prior and concomitant medication and radiotherapy will be listed.

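### SAP 6.4 and Table 4-1 set different boundaries for a prior medication, so a start on (or imputed to) the lacosamide start date is prior or not depending on whether the drug was later stopped

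*SAP*

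**What the plan says.** Four parts of the SAP bear on the prior flag.

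- SAP 6.4 gives the definition: "Prior medications are those medications started before the first dose of study drug". The same section includes chemotherapy and AEDs among the medications summarized. It counts a drug as concomitant if it is taken after the first dose, whenever it began.
- SAP 4.2.2, Table 4-1, gives rules that "will be applied in the case of completely missing stop and/or start date information". With a missing stop date, a drug whose start is "Before or on start date of LCM" is prior and concomitant. A drug that started later is concomitant only. With a missing start date, the drug is always prior, and it is also concomitant unless its stop precedes LCM.
- SAP 4.2.1 reads a missing stop date as follows: "If the end date is completely missing, then the medication or ADR are assumed to be ongoing". For a start with no day in the LCM start month, "the start day of the medication or ADR will be assigned to the day of first administration of LCM". For a year-only start in the LCM start year, "the start day and month will be assigned to the date of first administration of medication".
- SAP 4.8 summarizes both primary variables by prior tumor treatment, in levels that include chemotherapy alone and in combination, where a level has at least 25 patients. It does not say how prior is derived for that subgroup.

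**The concern.** Whether a drug was taken before LCM is a fact about its start. Under the current text, for a start on the LCM start date, the answer depends on its stop. A drug still running at the end of observation is prior. The same drug with the same start, stopped some months later, is not. The imputation rule adds to the problem, because it places partial start dates on the one day where the two rules disagree.

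What is at stake is the prior-medication table in SAP 6.4. The prior tumor treatment subgroup is also at stake if it is built from the same flag. There, a patient could be placed in a Baseline subgroup because of treatment status at Visit 3. Two programmers following the SAP could also reasonably produce different tables.

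**Working it through.** The only design figure is the sample size, and it does not depend on this flag. With p = 0.60 and a half-width of 0.10, n = 1.96² × 0.60 × 0.40 / 0.10² = 92.2, rounded up to 93. The half-width at 93 is 1.96 × √(0.24/93) = 0.0996. The plan's figure is reproduced and stays as it is.

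The check on the flag applies the rules as written to one drug, with an LCM start of 15 June 2016 (an assumed date, for illustration). The year-only rule in SAP 4.2.1 names the first administration of medication; it is read here as LCM.

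| Recorded start | Start used (4.2.1) | Prior if a stop after LCM start is recorded (6.4) | Prior if stop is missing (Table 4-1) |
|---|---|---|---|
| 14 June 2016 | 14 June 2016 | Yes | Yes |
| 15 June 2016 | 15 June 2016 | **No** | **Yes** |
| 16 June 2016 | 16 June 2016 | No | No |
| June 2016 | 15 June 2016 | **No** | **Yes** |
| 2016 | 15 June 2016 | **No** | **Yes** |
| May 2016 | 1 May 2016 | Yes | Yes |
| 2015 | 1 January 2015 | Yes | Yes |

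The rules agree in every row except the three where the start is, or becomes, the LCM start date. In those three the stop date alone decides. The drug is concomitant in both columns, so only the prior flag is affected. A partial stop date is completed under SAP 4.2.1, so such a record falls in the third column. Only a wholly missing stop reaches the disputed row of the table.

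One further case follows from the same imputation. Take a drug with start 2016 and a recorded stop of 1 June 2016. Its imputed start, 15 June, falls after its stop. Under SAP 6.4 it is not prior. It was not taken after the first LCM dose, so it is not concomitant either. Had the start been wholly missing, Table 4-1 would have called it prior. Here, recording more gives a worse classification.

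The documents do not give the number of same-day or partial starts, so the number of patients affected cannot be computed. The effect per patient can be illustrated, on the assumption that the SAP 4.8 subgroup uses this flag. Take a level of 25 patients with 15 responders: 60%, Clopper-Pearson 95% CI 38.7% to 78.9%.

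- One patient moved out: 14/24 = 58.3% if a responder, 15/24 = 62.5% if not.
- Three patients moved out: 12/22 = 54.5% if all are responders, 15/22 = 68.2% if none is.
- Any move out of a level of exactly 25 takes it below the display limit.

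These shifts lie well inside the interval for such a level.

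**The case against.** The strongest defence is that Table 4-1 is a special rule for missing dates, so it may differ from the general definition in SAP 6.4. That explains the split but does not justify it. In the disputed row the start date is available, and a missing stop date carries no information about whether the drug preceded LCM. It is also fair to say that this is a boundary mismatch confined to one calendar day and to the partial dates imputed to it, in a study with descriptive summaries only. That stands, and it keeps the point minor.

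Three stronger readings are tempting, and the documents do not support them.

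- A reader might infer that drugs and operations are handled in contradiction, because under SAP 4.2.3 "partial dates will be completed using the earliest calendar date based on the partial date provided". That section expressly exempts medication dates, so the difference is deliberate. The SAP states no prior rule for surgery or radiotherapy, and calling an operation prior would mean borrowing the medication wording of SAP 6.4. This is a gap in the plan and not a conflict.
- A reader might infer that the prior tumor treatment subgroup is in fact mis-sorted. SAP 4.8 does not say that it uses the medication flag. Protocol Table 15-1 collects tumor management as its own item, and SAP 6.2 lists concomitant procedures and procedure history separately. The case report form may therefore record prior and concomitant tumor treatment directly.
- A reader might want a share of patients misclassified. The documents give no basis for one, and it could be zero.

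The AED groupings are not affected by this flag: SAP 6.4 defines core AEDs by a form question and lifetime AEDs by an end date before the first LCM dose.

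**Conclusion.** The two boundaries conflict in the current text of the SAP. For a medication whose start equals, or is imputed to, the LCM start date, later stop status decides whether it is prior. The prior-medication summary, including chemotherapy, is affected directly. An effect on the prior tumor treatment subgroup is possible but conditional on how that subgroup is derived. The year-only results assume that the reference in SAP 4.2.1 to first administration of medication means LCM; the same-day and month-only results need no such assumption. The number of patients is unknown, the summaries are descriptive, and neither the overall primary results nor the sample size changes. This is a minor point, but it is a stated rule that departs from the plan's own definition and not merely missing detail, so it is worth correcting.

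**What to change.** 1. For complete start dates, use the SAP 6.4 boundary in Table 4-1. With a missing stop date, a start before the LCM start date is prior Yes, concomitant Yes; a start on or after it is prior No, concomitant Yes.
2. Amend SAP 4.2.1 and 4.2.2 together for medications with a partial start date that cannot be ordered against the LCM start. Count them as both prior and concomitant whatever their later stop date, and as prior and not concomitant if the recorded stop precedes LCM. This follows what Table 4-1 already does when the start is wholly missing. For classification it must replace the imputation to the LCM date; otherwise the revised table row would make the same record not prior. The date imputation for ADRs can stay as it is.

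The cost is two table rows and a short change to the text on partial dates, with no new data. The downside is that a few medications with unorderable dates will appear in both the prior and the concomitant summaries.

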4.2.3 General imputation rule for incomplete dates

Where necessary for the calculation of derived variables, partial dates will be completed using the earliest calendar date based on the partial date provided. This rule is valid for all partial dates with the exception of the following:

- Year is missing
- Start and stop dates of ADRs
- Start and stop dates of medications (see Sections 4.2.1 and 4.2.2)
- Start and stop dates of LCM
- Date of final contact
- Date of premature discontinuation

Incomplete dates for final contact and premature discontinuation, respectively, will be completed using the latest calendar date based on the partial date provided.

Start and stop dates of ADRs and LCM will not be imputed.

Completely missing dates or dates with a missing year will not be replaced, and the corresponding derived variables will be set to missing.

4.3 Interim analyses and data monitoring

No interim analysis or data monitoring board is planned in this NIS. Selected interim data may be reviewed periodically to detect as early as possible any safety concern(s) related to LCM and appropriately inform the treating physicians, patients, regulatory authorities, and/or Investigational Review Boards/Independent Ethics Committees.

4.4 Multicenter studies

Descriptive summaries for individual centers will not be presented. Subject data listings will provide data grouped by center.

4.5 Multiple comparisons/multiplicity

No formal statistical analyses will be performed on the primary endpoints. Therefore no adjustment for multiplicity is required.

4.6 Use of an efficacy subset of subjects

The modified FAS will be used to represent the on-label use of LCM.

4.7 Active-control studies intended to show equivalence

This is a single arm study and consequently this section is not applicable.

4.8 Examination of subgroups

The primary endpoints will be summarized by the following subgroups, if at least 25 patients fall into that subgroup:

- Starting dose of LCM (high starting dose - first dose ≥ 200 mg/day; titration – first dose < 200 mg/day)
- Prior tumor treatment (radiotherapy; chemotherapy; surgery; radiotherapy and chemotherapy; radiotherapy and surgery; chemotherapy and surgery; radiotherapy, chemotherapy and surgery)
- Concomitant tumor treatment (radiotherapy; chemotherapy; surgery; radiotherapy and chemotherapy; radiotherapy and surgery; chemotherapy and surgery; radiotherapy, chemotherapy and surgery)
- Number of different types of lifetime AEDs (1; 2; 3; 4)
- Core AED therapy (including but not limited to levitiracetam, valproate sodium, lamotrigine, oxcarbazepine, zonisamide, topiramate, pregabalin, gabapentin, phenytoin, carbamazepine, clonazepam, clobazepam, phenobarbital, valproic acid, ergenyl chrono; combinations of these therapies)

Note: Each subject can be only in 1 category for "Core AED therapy"

- Age (≥ 16 - ≤ 18 ; > 18 - < 65 ; ≥ 65)
- Sex (male; female)
- Historical seizure frequency (1; 2-5; 6+)
- Historical seizure type (Partial-onset seizures with secondary generalization; Partial-onset seizures without secondary generalization; Both)
- Time since tumor diagnosis (≤ 1 month; > 1 - ≤ 3 months; > 3 - ≤ 6 months; > 6 months - ≤ 12 months; > 12 - ≤ 24 months; > 24 months)
- Type of brain tumor (astrocytoma; oligodendrolioma; mixed [oligo-astro]; ependymoma; other)
- WHO grade (1; 2; 3; 4)
- Karnofsky performance status (<60%; 60%; 70%; 80%; 90%; 100%)

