1 RATIONALE FOR THE STUDY

Patients with brain tumor-related epilepsy (BTRE) present a complex therapeutic profile and require a unique and multidisciplinary approach. There are many factors to take into consideration, especially the management of epilepsy, which is often considered the most important risk factor for long-term disability (Maschio, 2012).

In patients with brain tumors, seizures are the onset symptom in 20-40% of patients, while a further 20-45% of patients will present with seizures during the course of the disease. Overall, the incidence of epilepsy in brain tumors, regardless of histological type and anatomical site of the lesion, varies from 35 to 70% (Rossetti and Stupp, 2010; Vecht and Wilms, 2010; Singh et al, 2007; Hildebrand et al, 2005; Wen and Marks, 2002; Glantz et al, 2000).

Lacosamide (LCM, VIMPAT[®]) is an antiepileptic drug (AED), which has been shown to provide a favorable benefit-risk profile and was approved by the European Medicine Agency (EMA) on 29 Aug 2008 (EU/1/08/470/01 to 013 and EU/1/08/470/016 to 023; EMA reference EMEA/H/C/000863) as adjunctive therapy in the treatment of partial-onset seizures with or without secondary generalization in patients with epilepsy aged 16 years and older (film-coated tablets of 50mg, 100mg, 150mg, and 200mg, syrup of 10mg/mL, and solution for infusion of 10mg/mL). In addition to the European Union, LCM is approved as adjunctive therapy in adults suffering from partial-onset seizures in at least 38 other countries to date. In the United States, LCM is approved as adjunctive therapy or monotherapy in patients age 17 years and older and suffering from partial-onset seizures.

The pharmacokinetic profile of LCM includes minimal cytochrome P450 interaction and low (<15%) protein binding, resulting in a low risk for drug-drug interaction (Lacosamide Summary of Product Characteristics, 2011). This is particularly important in the context of BTRE, since many chemotherapeutic agents are susceptible to metabolism via the P450 pathway, as are a number of AEDs which may be co-prescribed during the natural history of disease.

Lacosamide has been shown to be efficacious and generally well tolerated in real life clinical practice, from first adjunct to later treatment lines (Stephen et al, 2011; Villanueva et al, 2012).

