15 RECOMMENDED SCHEDULE OF STUDY ASSESSMENTS

Table 15–1: Recommended schedule of study assessments

Assessments	Visit 1 ^a (Baseline)	Visit 2 Approximately 3 months after Baseline according to routine practice ^b	Visit 3 (End of Observation Period or Withdrawal Visit ^c) Approximately 6 months after Baseline according to routine practice ^b
Signed data consent	X		
Demographic data	X		
Medical history	X ^d		
Seizure history	X ^d		
Tumor diagnosis and grade (including review of most recent brain imaging results [CT or MRI])	X		X
Prior and concomitant tumor management (surgical procedures, chemotherapies, radiotherapy)	X ^d		X
Prior and concomitant AEDs	X	X	X
Other prior and concomitant epilepsy treatment	X	X	X
Other prior and concomitant relevant medications	X ^d	X	X
Verification of selection criteria	X		
Documentation of LCM administration	X	X	X
Documentation of seizure information (including seizure frequency and type) ^e		X	X
Karnofsky performance status	X	X	X
EQ-5D-5L	X		X

Table 15–1: Recommended schedule of study assessments

Assessments	Visit 1 ^a (Baseline)	Visit 2 Approximately 3 months after Baseline according to routine practice ^b	Visit 3 (End of Observation Period or Withdrawal Visit ^c) Approximately 6 months after Baseline according to routine practice ^b
MDASI-BT	X		X
PGIC			X
CGIC			X
Recording of ADRs and AESIs	X	X	X
Withdrawal criteria		X	X

ADR=adverse drug reactions; AED=antiepileptic drug; AESI=adverse event of special interest; CGIC=Clinical Global Impression of Change; CT=computerized tomography; EQ-5D-5L=5-Level EuroQol-5 Dimension Quality of Life Assessment; LCM=lacosamide; MRI=magnetic resonance imaging; MDASI-BT=M.D. Anderson Symptom Inventory - Brain Tumor; PGIC=Patient Global Impression of Change

^a Visit 1 will be performed after the decision is taken to start adjunctive LCM therapy. Treatment with LCM should be initiated according to routine clinical practice. If the first dose of LCM is given on the same day as Visit 1, it should be administered after Baseline assessments are complete. Previous treatment with LCM is allowed for up to 7 days prior to enrollment.

^b The frequency of visits after Visit 1 will be based on local clinical practice and the patients' requirements. The clinical procedures performed at each visit will also follow local clinical practice. It is estimated that patients will be followed at least every 3 months.

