3.3 Definition of Baseline values

Concomitant AEDs at Baseline are defined as AEDs given at the start date of LCM or the date of Visit 1 in case of a missing start date of LCM.

For all other variables, Baseline data are the values collected at Visit 1.

Baseline for the partial-onset seizure frequency per 28 days will be derived from the data of the Historical Seizure Count form as described in Section 3.10.4.

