6.2 Other Baseline characteristics

The following characteristics will be summarized at Baseline:

- Time since tumor diagnosis (years) – continuous
- Type of brain tumor (astrocytoma, oligodendrolioma, mixed [oligo-astro], ependymoma, other)
- Tumor (WHO) grade (1, 2, 3, 4)
- Karnofsky performance status

Details of concomitant procedures and procedure history will be listed. Karnofsky performance status and tumor characteristics will also be listed at Baseline and post-Baseline assessments.

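### The concomitant-tumor-treatment subgroup can be decided by treatment begun after the first LCM dose, so its response and PGIC rates may not describe patients who were on tumor treatment when LCM started

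*SAP*

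**What the plan says.** - SAP 4.8 lists the subgroups for the primary endpoints. One is "Concomitant tumor treatment (radiotherapy; chemotherapy; surgery; radiotherapy and chemotherapy", continuing to seven single or combined modalities. It has no time window and no level for patients without tumor treatment. A subgroup is shown only if it holds at least 25 patients.
- SAP 8.1.2.1 gives the responder rate with a Clopper-Pearson 95% CI in each subgroup. SAP 8.1.2.2 does the same split for PGIC, without a CI.
- SAP 6.4 supplies the only definition of concomitant, with the first LCM dose as its reference point: "Medication taken after the first dose of study medication will be regarded as concomitant medication whether the start date is before, after or on". It covers "prior and concomitant medications (including chemotherapy and AEDs". SAP Table 4-1, which handles missing dates, agrees: a medication started after LCM is concomitant and not prior.
- For radiotherapy SAP 6.4 says only: "The number and percentage of patients who had prior or concomitant radiotherapy will be summarized". For surgery SAP 6.2 says: "Details of concomitant procedures and procedure history will be listed". Neither gives a time rule.
- Protocol Table 15-1 has a row "Prior and concomitant tumor management (surgical procedures, chemotherapies, radiotherapy", marked at Visit 1 and again at Visit 3 or withdrawal.
- Where the SAP means status at LCM start, it says so. SAP 3.3: "Concomitant AEDs at Baseline are defined as AEDs given at the start date of LCM".

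**The concern.** A subgroup meant to describe response in a kind of patient should be fixed when treatment starts. This one mixes patients already on tumor treatment at the first LCM dose with patients who began it during follow-up. The second kind may be selected by the course of the disease, since progression or worsening seizures can both prompt tumor treatment and lower response or PGIC. They are also selected by time in study, since someone who leaves early has less time to acquire a treatment.

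The table will attract attention. Protocol section 1 bases part of the rationale on low interaction risk, noting that "many chemotherapeutic agents are susceptible to metabolism via the P450 pathway". A reader who wants to know how patients do on LCM together with chemotherapy will look here and may take the rate as the answer.

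**Working it through.** **The plan's own figure.** SAP 2.4: half-width = 1.96 × √(0.60 × 0.40 / 93) = 0.0996, the stated 0.10. It reproduces and is not in dispute.

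**What the text fixes.** For chemotherapy, SAP 6.4 explicitly admits starts after the first dose. For radiotherapy and surgery this is an inference from the shared label and the Visit 3 collection. Treatment ongoing at the first dose also counts, so membership is only partly post-Baseline.

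**Illustration A: treatment prompted by progression.** The documents give no progression or tumor-treatment rates, so these are assumptions:
- 25% are on tumor treatment at LCM start, unrelated to outcome.
- 15% progress, and 70% of progressors not already treated then start treatment.
- Response is 30% in progressors and 65% in others. Overall: 0.15 × 0.30 + 0.85 × 0.65 = 59.75%, close to the planned 60%.

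Steps:
1. Ever treated after the first dose: progressors 0.25 + 0.75 × 0.70 = 0.775; others 0.25.
2. Share treated: 0.15 × 0.775 + 0.85 × 0.25 = 0.11625 + 0.2125 = 0.32875, or about 31 of 93.
3. Response with treatment: (0.11625 × 0.30 + 0.2125 × 0.65) / 0.32875 = 52.6%.
4. Response without: (0.03375 × 0.30 + 0.6375 × 0.65) / 0.67125 = 63.2%.
5. Gap: -10.6 points. Split by status at the first dose, both groups respond at 59.75% and the gap is 0.

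Changing one input at a time, with others kept at 65%:

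| Change | With | Without | Gap |
|---|---|---|---|
| Progressors respond at 45% | 57.9% | 64.0% | -6.1 |
| 20% progress | 49.7% | 62.6% | -12.8 |

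Since SAP 4.8 has no untreated level, the likelier comparison is with the overall rate: 52.62 - 59.75 = -7.1 points.

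**Illustration B: unequal time in study.** Assume 20% leave early, uniformly over 180 days, with 20% response; completers respond at (0.60 - 0.20 × 0.20) / 0.80 = 70%. Tumor treatment starts at a constant rate reaching 20% over 180 days and has no effect on response. Nobody is on it at LCM start.
1. Early leavers start treatment with probability 1 - 0.20 / 0.2231 = 0.1037, where 0.2231 = -ln 0.80; completers with 0.20.
2. Share treated: 0.20 × 0.1037 + 0.80 × 0.20 = 0.1807.
3. Response with treatment: (0.02074 × 0.20 + 0.16 × 0.70) / 0.1807 = 64.3%.
4. Response without: (0.60 - 0.1807 × 0.643) / 0.8193 = 59.1%.

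The gap is about +5 points, opposite in sign to A. With 10% to 30% leaving early, 20% to 40% response among them and 20% to 40% starting treatment, the treated group shows roughly 62% to 67% against 57% to 60%. Treatment ongoing at LCM start dilutes this.

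**Null case.** If starting treatment is unrelated to response and to time in study, both groups show 60%.

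**Precision.** At the 25-patient minimum, 15 of 25 responders gives a Clopper-Pearson interval of 38.7% to 78.9%. The interval reflects sampling error only, not the selection described here.

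**The case against.** A reader might infer that these subgroup rates are biased in a known direction, that the surgery level is wholly post-Baseline, or that the study will report a spurious treated-versus-untreated difference. The documents do not support any of these.

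- **Direction.** Illustrations A and B have opposite signs, and every rate in them except the 60% is assumed. B also shrinks if early leavers have no Visit 3 value, because the percentages use available data only.
- **Surgery and radiotherapy.** The written time rule is for medication. How the case report form labels recent surgery is not in the documents. LCM may also start up to 7 days before enrollment, so surgery after the first dose could still precede Visit 1.
- **The contrast.** No any-versus-none comparison is planned. About 31 of 93 treated patients spread over seven levels would rarely fill a row: one level would need 25 / 30.6, about 80% of them. A surgery-only row would need 25 / 93, or 27%, operated on in about 6 months.
- **Status.** The SAP is descriptive and tests nothing, and medication, radiotherapy and procedures are listed patient by patient. A Baseline-fixed subgroup in a single-arm study would still be confounded.

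All of this stands and limits the point. It does not remove it. The chemotherapy rule is explicit, and the other two modalities have no stated window at all. A percentage with a CI under a subgroup heading will be read as response in that kind of patient, even where nothing is tested. Post-Baseline starters also help a level reach 25 and so be printed.

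**Conclusion.** The point holds in limited form. As written, this subgroup can be set by events after the first LCM dose that are linked to response, PGIC and length of stay. Its rates, and the CIs for response, may therefore not describe patients who were on tumor treatment when LCM began. That is certain from the text for chemotherapy and inferred for radiotherapy and surgery.

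Size and direction are unknown. The -10.6 points (-6.1 and -12.8 in the variations) shows what the definition could do under the stated assumptions; it is not an estimate for this study. The consequence is confined to interpreting one descriptive subgroup table per primary variable. The change is worth making because it is cheap and the table bears on the study's rationale.

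**What to change.** In SAP 4.8 replace the row with *Tumor treatment ongoing at first LCM dose*, with levels none, chemotherapy, radiotherapy, and both. Ongoing means started on or before the first LCM dose and not stopped before it, judged on reported dates.

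Do not use the imputed start day from SAP 4.2.1 for this flag. That rule sets a missing start day to the day of the first LCM dose when month and year match, so chemotherapy begun later that month would be counted as ongoing. Show cases that cannot be determined separately.

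Report chemotherapy, radiotherapy or surgery started after the first LCM dose in its own descriptive row, labelled as a post-Baseline event and not as a subgroup for response to LCM.

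The cost is SAP wording and one derived flag, from dates the prior/concomitant split already needs. No data collection, sample size or patient care changes. The downside is smaller groups: under the assumptions of illustration A, 0.25 × 93, about 23 patients, would be on treatment at the first dose, so some levels may miss the 25-patient minimum.
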